11.3 Serious adverse events (SAEs)

11.3.1 Definition SAE

A serious adverse event is any untoward medical occurrence or effect that:

- results in death;
- is life threatening (at the time of the event);
- requires hospitalization or prolongation of existing in-patients' hospitalization;
- results in persistent or significant disability or incapacity;

- is a congenital anomaly or birth defect;
- any other important medical event that did not result in any of the outcomes listed above due to medical or surgical intervention but could have been based upon appropriate judgement by the investigator.

An elective hospital admission will not be considered as a serious adverse event.

11.3.2 Reporting SAEs

SAEs must be reported to the research team of the Hematology department of the UMCU within 24 hours by email [contact] after the event was known to the investigator, using the SAE report form provided. This initial report should contain a minimum amount of information regarding the event, associated treatment and patient identification, as described in the detail in the instructions for the SAE report form. Complete detailed information should be provided in a follow-up report within a further 2 business days, if necessary.

The sponsor (UMCU) will report the SAEs through the web portal ToetsingOnline to the accredited EC that approved the protocol, within 7 days of first knowledge for SAEs that result in death or are life threatening followed by a period of maximum of 8 days to complete the initial preliminary report. All other SAEs will be reported within a period of maximum 15 days after the sponsor has first knowledge of the serious adverse events.

11.3.3 Causality assessment of SAEs

The investigator will decide whether the SAE is related to the study treatment. The assessment of causality is made by the investigator using the following:

RELATIONSHIP	DESCRIPTION
UNRELATED	There is no evidence of any causal relationship
UNLIKELY	There is little evidence to suggest there is a causal relationship (e.g. the event
	did not occur within a reasonable time after administration of the trial
	medication). There is another reasonable explanation for the event (e.g. the
	patient's clinical condition, other concomitant treatments).
POSSIBLE	There is some evidence to suggest a causal relationship (e.g. because the
	event occurs within a reasonable time after administration of the trial
	medication). However, the influence of other factors may have contributed to the
	event (e.g. the patient's clinical condition, other concomitant treatments).
PROBABLE	There is evidence to suggest a causal relationship and the influence of other
	factors is unlikely.
DEFINITELY	There is clear evidence to suggest a causal relationship and other possible
	contributing factors can be ruled out.
NOT	There is insufficient or incomplete evidence to make a clinical judgement of the
ASSESSABLE	causal relationship.

11.4 Suspected unexpected serious adverse reaction (SUSAR)

Unexpected adverse reactions are SUSARs if the following three conditions are met:

- 1. the event must be serious (see chapter 11.3.1.);
- there must be a certain degree of probability that the event is a harmful and an undesirable reaction to the medicinal product under investigation, regardless of the administered dose;
- 3. the adverse reaction must be unexpected, that is to say, the nature and severity of the adverse reaction are not in agreement with the product information as recorded in:
 - a. the SPC for an authorised medicinal product;
 - b. Investigator's Brochure for an unauthorised medicinal product.

SUSARs must be reported to the research team of the Hematology department of the UMCU within 24 hours by email [contact] after the event was known to the investigator, using the SAE report form provided

The sponsor (UMCU) will ensure the reporting of any SUSARs to the Ethics Committees (EC), the Competent Authorities (CA) and the investigators in compliance with applicable laws and regulations.

The sponsor will report expedited all SUSARs to the competent authorities in other Member States, according to the requirements of the Member States.

The expedited reporting will occur not later than 15 days after the sponsor has first knowledge of the adverse reactions. For fatal or life threatening cases the term will be maximal 7 days for a preliminary report with another 8 days for completion of the report.

11.5 Annual safety report

In addition to the expedited reporting of SUSARs, the sponsor (UMCU) will submit, once a year throughout the clinical trial, a safety report to the accredited Ethics Committees, competent authority, and competent authorities of the concerned Member States.

This safety report consists of:

- a list of all suspected (unexpected or expected) serious adverse reactions, along with an aggregated summary table of all reported serious adverse reactions, ordered by organ system, per study;
- a report concerning the safety of the subjects, consisting of a complete safety analysis and an evaluation of the balance between the efficacy and the harmfulness of the medicine under investigation.

11.6 Follow-up of adverse events

All adverse events will be followed until they have abated, or until a stable situation has been reached. Depending on the event, follow up may require additional tests or medical procedures as indicated, and/or referral to the general physician or a medical specialist. Follow-up reports on SAEs will be added to the reported SAEs on *ToetsingOnline*.

11.7 Data Safety and Monitoring Board

The Data and Safety Monitoring Board will advise the Principal Investigator and the Coinvestigator(s) about the continuation of the study. The DSMB will evaluate the general progress and the feasibility of the study, the quality and completeness of the data, side effects and safety.

The DSMB consists of at least 3 members, among whom (at least) one statistician and minimally two physicians. The members of the DSMB are invited on personal title on the basis of their expert knowledge of the disease involved or the research methodology. Members of the DSMB will have ample experience with randomized clinical trials. The members of the DSMB will not be involved in the study or work in a hospital department participating in the study. The members will not have a conflict of interest due to ties with a company involved in the study.

The DSMB reports their written recommendations to the Principal Investigator and the Coinvestigator(s). The DSMB recommendations are not binding. Should the sponsor (UMCU)decide not to fully implement the advice of the DSMB, the sponsor will send the advice to the reviewing Ethics Committees, including a note to substantiate why (part of) the advice of the DSMB will not be followed.

The DSMB will receive at least the following reports from the trial statistician for review:

- Annual safety data listing the incidence of (serious) adverse events and (serious) adverse reactions
- Annual progress data listing the number of enrolled patients and the status of data collection
- Annual report on safety outcomes

STATISTICAL CONSIDERATIONS

12.1 Patient numbers and power considerations

The aim of the randomization is to evaluate whether addition of targeted fludarabine results in a reduction of the incidence of severe viral infections. For the primary endpoint, patients will be considered a success if they did not develop serious infections within 100 days posttransplant while being alive, relapse-free. Based on the retrospective data, we hypothesize that 40 % of the subjects treating according to arm A will experience serious infections. To detect a 25% reduction of failures with arm B with a power of 80%, each arm should consist of 42 patients evaluable at day 100. This is based on the assumption that 10% of patients in each arm will not contribute to the primary analysis due to death or relapse. This leads to an assumed proportion of failures of 40/90=0.4444444 in arm A and 15/90=0.1666667 in arm B (2-sided significance level of 0.05, Z test with pooled variance, power=81%). To compensate for non-evaluability due to death, relapse or other reasons, 15% extra patients per arm will be included, leading to a total sample size of 2 times 49, is 98 patients.

12.2 Safety

With respect to safety, a yearly report as described in 11.5 and 11.7 will be submitted to the EC and DSMB. In case 20 patients reach the 100 days follow-up before 1 year, the DSMB will be informed earlier. The yearly report will contain NRM, OS and relapse rates. In addition we will report the reportes (S)AEs and SUSARs. All patients will be considered in the safety analysis. Patients will be closely followed for unexpected toxicities and, if any serious side effects are observed, the investigators will reevaluate the appropriate course for the study. At the conclusion of the study, all unexpected toxicities will be summarized and reported. If the DSMB recommends to stop the study based on the safety outcomes, the sponsor (UMCU) Version 1.1 | 02 AUG 2018

will follow the advice of the DSMB or discuss with the EC requirements for continuation of the study.

12.3 Interim analysis

No interim analysis will be performed. Yearly reports will be submitted to the DSMB.

12.4 Statistical analysis plan

All analyses will be done in accordance with the intention-to-treat principle in all patients who have initiated the study treatment, when the last patient is 100 days post transplantation or has gone 'off-protocol'.

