
NL64877.041.18 | TARGET Study

Primary Objective: To address whether the individualized fludarabine conditioning reduces

the incidence of severe viral infections at day 100 within the context of an $\alpha\beta TCR$ / CD19

depleted transplantation regimen.

Secondary Objective: To address whether the individualized fludarabine conditioning

affects other clinical transplantation-related parameters, variations in individual fludarabine

exposures and immunological reconstitution after an $\alpha\beta$ TCR/CD19 depleted stem cell

transplantation.

Study design: Prospective, multicenter, open label randomized, phase II study

Study population: Patients with a selected range of hematological malignancies eligible for

allogeneic stem cell transplantation.

Intervention: Patients will be randomized to either to standard dosing of fludarabine or

individualized fludarabine dosing as part of a conditioning regimen, followed by an αβTCR /

CD19 depleted transplantation.

Target number of patients: 98 randomized

Expected duration of accrual: 2 years

Main study parameters/endpoints:

Primary Endpoint:

Cumulative incidence of severe viral infections at day 100.

Secondary Endpoints:

Non relapse mortality (NRM) at day 100

aGVHD grade II-IV at day 100

Donor engraftment (chimerism > 95%) at day 100

Overall survival at day 100

Cumulative incidence of relapse at day 100

Effective fludarabine exposure

Nature and extent of the burden and risks associated with participation, benefit and

group relatedness:

The protocol comprises a different dosing of fludarabine in the experimental arm. All other acts, measurements, follow-up and level of care are therefore similar to off-study patients undergoing allo-SCT. The burden of the therapy is associated with the allo-SCT itself, which is a necessary therapeutic intervention in all subjects. Possible increased risks for the recipient are graft failures, though not observed so far in all cohorts with the intended dose levels. The intended target level of fludarabine remains in the range of all so far treated patients at the UMCU. We only propose to avoid too high exposure to fludarabine. Possible benefits include a proposed lower incidence of infections, low incidence of GVHD as well as optimized cancer surveillance due to a more balanced immune reconstitution.

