5. OBJECTIVE

5.1 Primary endpoint:

Cumulative incidence of severe viral infections (≥ grade 2 as in APPENDIX E) until day
 100

5.2 Secondary Endpoints:

- Engraftment
 - Time to neutrophil engraftment
 - Time to platelet engraftment
 - Donor engraftment (chimerism > 95%) at day 100
- Clinical outcome
 - o aGVHD until day 100
 - NRM until day 100
 - Number of graft failures until day 100
 - Event free survival (EFS: i.e. time from transplantation until progression/relapse, graftfailure or death from any cause, whichever comes first)
 - Overall survival (OS) calculated from transplantation. Patients still alive or lost to follow up are censored at the date they were last known to be alive Incidence of infections
 - Incidence and grade of chronic GvHD

- Long term NRM (1Y)
- Long term (secondary) graft failure (1Y)
- PK/PD
 - o ATG exposure
 - Fludarabine exposure
 - o Busulfan exposure
- Immunoreconstitution
 - Immune reconstitution including but not limited to total number of CD3⁺ T cells, CD4⁺ and CD8+ subtyping of T cells, CD3-CD16/56+ (NK cells), γδT-cells at 3, 6, 12 and 24 months after transplantation, assessment of NK and TCR repertoires at defined time points with personalized fludarabine conditioning.
 - Graft composition (CD34+ cells, αβ T cells, γδ T cells, NK cells, B cells)

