6. STUDY DESIGN

This is a multicenter prospective, open label randomized, phase II study (UMCU (Utrecht), LUMC (Leiden), Johannes Gutenberg University (Mainz)). Patients with hematological malignancies according to the inclusion criteria with a matched related donor or a matched unrelated donor, are treated with a $\alpha\beta$ TCR / CD19 depleted allo-SCT. Conditioning regimes are depicted on 8.3 which differ only in:

Arm A: Fludarabine based on classical dosing

Arm B: Individualized fludarabine aimed to avoid overexposure (section 9)

All other interventions, except for alternate dosing of fludarabine in arm B, are considered as standard of care. All subjects will complete the end of treatment visit at day 100. After day 100, subjects will enter an extended follow-up of 1 year.

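### Section 12.4 times every analysis at day 100 of the last patient, although Section 5.2 lists 1-year and month-12 endpoints; the 24-month immune time point also has no visit in the schedule grid

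*Protocol*

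**What the plan says.** Section 12.4 of the protocol opens with a rule on population and timing: "All analyses will be done in accordance with the intention-to-treat principle in all patients who have initiated the study treatment", and this is to happen "when the last patient is 100 days post transplantation". The only alternative trigger is that the last patient has gone off protocol. No endpoint is exempted.

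Section 5.2 lists secondary endpoints that need longer follow-up. NRM and secondary graft failure are each dated at 1 year. Immune reconstitution is to be assessed at "3, 6, 12 and 24 months after transplantation".

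On follow-up, Section 6 states: "After day 100, subjects will enter an extended follow-up of 1 year". The schedule in Section 10.4 has visits to month 12 that include disease, GVHD and immune assessments. After month 12 its only column is a six-monthly survival contact.

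No later analysis is described. Section 12.3 plans no interim analysis, and the yearly reports in Sections 11.7 and 12.2 concern safety and progress. Section 15.4 ties the end of study to the final visit of the last patient and requires a final report within a year after that, but sets no second data cut.

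**The concern.** Followed literally, the timing rule means the 1-year endpoints are analysed before many late-enrolled patients can have been observed for a year, although the trial goes on to collect those data.

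Two of the affected endpoints bear on safety. Section 9.3 names graft failure as the main risk of too low fludarabine exposure, and Section 9.2.1 reports more graft failures at lower exposures. Late graft failure and late NRM are therefore results a reader will want in full for the individualised arm. Month-12 immune counts bear on the proposed mechanism.

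The 24-month immune time point raises a different problem: the documents disagree on whether anything is collected then.

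**Working it through.** **The plan's own figure.** The protocol gives no figure for the share of patients with 1-year follow-up at the analysis, so there is none to reproduce. Its sample size concerns the day-100 endpoint only. With failure proportions 40/90 and 15/90, two-sided 0.05 and a pooled Z test, the recalculation gives 42 per arm with power 80.0%, against the stated 42 and 81%. Nothing below changes that.

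**Inputs**
- Accrual: "Expected duration of accrual: 2 years" (Synopsis), taken as A = 730 days.
- Patients: "Target number of patients: 98 randomized" (Synopsis), N = 98.
- Cut: day 100 of the last patient (Section 12.4), that is, day A + 100 on the trial calendar.
- Horizons: F = 365 days for the 1-year endpoints and F = 730 days for the 24-month time point (Section 5.2).
- Assumption not in the protocol: transplants are spread uniformly over the accrual period.

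**Share unable to reach the horizon.** A patient transplanted on day t has A + 100 − t days of potential follow-up at the cut. This is below F when t falls in the last F − 100 days of accrual. The share is therefore (F − 100)/A.
- 1 year: (365 − 100)/730 = 265/730 = 36.3%; 0.363 × 98 ≈ 36 patients.
- 1 year, counting a visit at the early edge of the 3-week window: (344 − 100)/730 = 33.4%, about 33 patients.
- 24 months: (730 − 100)/730 = 86.3%, about 85 patients.

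**How far the 1-year share depends on the accrual assumption**

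| Accrual pattern | Share short of 1 year | Of 98 |
|---|---|---|
| Uniform, 18 months | 48% | 47 |
| Uniform, 24 months | 36% | 36 |
| Uniform, 30 months | 29% | 28 |
| Uniform, 36 months | 24% | 24 |
| Linear ramp-up, 24 months: 1 − (465/730)² | 59% | 58 |
| Linear ramp-down, 24 months: (265/730)² | 13% | 13 |

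**Information lost for the event endpoints.** Under uniform accrual the affected patients fall short by 0 to 265 days, on average 132.5 days. The lost share of first-year potential person-time is 0.363 × 132.5/365 = 13%. Every transplanted patient still contributes up to day 100. Section 12.4.2 estimates competing-risk outcomes by cumulative incidence, which accommodates this kind of censoring.

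**Information lost for month-12 counts.** A cell count at a fixed visit has no such remedy. At this cut it is absent for every patient who has not reached the visit, up to about 36 of 98.

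**The 24-month time point, places side by side**
- Section 5.2 asks for immune reconstitution at 24 months.
- Section 6 describes an extended follow-up of 1 year.
- The Section 10.4 grid stops immune monitoring and biological sampling at month 12.
- Section 10.3.4 follows patients until relapse or progression, with no limit in time.
- Footnote xi to the schedule makes immune monitoring monthly after discharge, with no end date.

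The first item and the last two are compatible with a month-24 sample; the other two are not.

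**The case against.** The strongest defence is that day 100 is the deliberate focus. The introduction separates toxicity up to day 100 from longer-term questions, and every dated secondary endpoint in the Synopsis is at day 100. Month-12 visits continue whatever the cut, and the Section 15.4 final report falls after they are complete. A statistical analysis plan, not shown here, could also add a later cut. Much of this is fair: the data will exist. But the protocol is not silent on timing. It places all analyses at day 100, so a later plan with a 1-year analysis would depart from it, and Section 15.4 promises no re-analysis.

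The figure of 36% could also be read as the loss of information on 1-year NRM and graft failure. It is not; under uniform accrual that loss is about 13% of first-year person-time. Some of the 36 patients would in any case die, relapse or lose their graft before month 12. Under Section 10.7, relapse and graft failure lead to follow-up for survival only, so a later cut would not recover those patients' counts.

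A reader might infer three stronger points that the documents do not support:
- **That chronic GVHD, EFS and OS contradict the cut as well.** Section 5.2 attaches no 1-year date to them, so they do not.
- **That chronic GVHD incidence would be missing for late-enrolled patients.** It can be estimated by cumulative incidence with those patients censored.
- **That the 24-month immune value will never be collected.** Section 10.3.4 and footnote xi give no end date. The documents conflict; they do not rule collection out.

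**Conclusion.** The point holds. The single day-100 cut in Section 12.4 does not fit the 1-year NRM, 1-year secondary graft failure and month-12 immune reconstitution endpoints in Section 5.2. Under uniform 2-year accrual about 36 of 98 patients could not have reached 1 year. That accrual pattern is an assumption, and the share could be 13% or 59% under the linear alternatives, but a gap remains in every pattern tried. The consequence is reduced precision for the two event endpoints and real missingness only for month-12 measurements. The off-protocol trigger could only bring the cut forward, so it does not help. The primary endpoint, the sample size and the day-100 secondary endpoints are untouched.

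The 24-month immune time point is a separate inconsistency between Sections 5.2, 6, 10.3.4 and 10.4. Even if samples were taken, about 86% of patients could not have reached that time point at the stated cut.

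**What to change.** In Section 12.4, keep the day-100 cut for the primary and day-100 secondary endpoints. Add one sentence stating a second analysis when the last patient has completed the month-12 visit, covering 1-year NRM, 1-year secondary graft failure and month-12 immune reconstitution. Chronic GVHD, EFS and OS can be updated at the same cut. This brings the share short of 1 year from 36% to zero.

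The cost is one sentence and one further data cut, using visits already in the schedule. The 1-year results come 365 − 100 = 265 days later, about 9 months; the day-100 results are not delayed.

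Separately, reconcile Sections 5.2, 6, 10.3.4 and 10.4 (grid and footnote xi) on how long immune monitoring runs. Either remove the 24-month time point from Section 5.2, which costs one deletion, or add a month-24 immune visit to the grid with a matching analysis time. The second option would put that analysis 730 − 100 = 630 days after the day-100 cut.

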12.4.1 Primary endpoint

The primary endpoint is the probability of serious viral infections up to 100 days after transplantation for patients alive relapse-free at 100 days. This endpoint will be analyzed in a poisson regression model including treatment arm and the stratification factors used in the randomization.

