No graft failures have been observed. The incidence of aGVHD grade III-IV at day 100 was 5.6% (n=1) in prospective cohort and 0% in retrospective cohort (data not shown). In the combined retrospective and prospective cohort, the CI of aGVHD II-IV is 17% at day 100, the CI of viral infections > grade III was 38% at day 100 and the combined CI of aGVHD grade II-IV and viral infections \geq grade III was 47% at day 100 (Figure 1). Amongst the viral grade III infections, 2 cases of PTLD (2.5%) were observed.

[^] Intermediate cytonetics n= 2; adverse cytonetics n=2

[#] DLBCL/Transformed B-NHL n=1

[~] plasmacelleukemia n=2

[figure not shown]

Figure 1: CI of grade II-IV aGVHD (A), viral infections \geq grade III (B) and combined CI of aGVHD II-IV or viral infections \geq grade III (C). Death and relapse are competing events. Pooled data of retrospective and prospective cohort (n=75). Viral infections can be either CMV, EBV or BK. Grading is performed according to CTC-AE V4.0. Grade III implies either an infection requiring i.v. medication or admission to the hospital.

Efficacy was analyzed in the retrospective cohort, given the short follow-up of the prospective cohort. With a median follow-up of 13 months, the 2-year (2Y) event free survival (EFS) was estimated to be 61% and the overall survival (OS) to be 65%. The cumulative relapse incidence was 25% and the NRM 14% (Figure 2). Interestingly, long term survivors had a very low incidence of cGVHD despite multiple DLIs, suggesting that this platform does not only allow early immune interventions but also associates with a rather low long-term toxicity (Figure 3A).

[figure not shown]

Figure 2: Overall survival (A), EFS (B), cumulative incidence of relapse (C) and NRM (D) of retrospective cohort. Cause of NRM see below.

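### The primary analysis is limited to patients alive and relapse-free at day 100, which conflicts with the cumulative-incidence endpoint and with intention to treat, and the power rests on the same restriction

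*Protocol*

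**What the plan says.** The synopsis gives the primary endpoint as "Cumulative incidence of severe viral infections at day 100", and section 5.1 as "Cumulative incidence of severe viral infections (≥ grade 2 as in APPENDIX E) until day" 100. Neither limits it to survivors. Section 12.4 states: "All analyses will be done in accordance with the intention-to-treat principle in all patients who have initiated the study treatment".

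Section 12.4.1 then sets the primary endpoint as "the probability of serious viral infections up to 100 days after transplantation for patients alive relapse-free at 100 days".

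Section 12.1 says "patients will be considered a success if they did not develop serious infections within 100 days posttransplant while being alive, relapse-free". It starts from an all-patient rate ("we hypothesize that 40 % of the subjects treating according to arm A will experience serious infections"), assumes that 10% per arm drop out of the primary analysis through death or relapse, and divides by the rest: "This leads to an assumed proportion of failures of 40/90=0.4444444 in arm A and 15/90=0.1666667 in arm B". It requires 42 evaluable patients per arm and adds 15%, giving 49 per arm and 98 in total.

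The historical rate of 38% at day 100 in section 4.1.2 was obtained differently. It pools all 75 patients, and the figure legend notes: "Death and relapse are competing events". Section 12.4.2 treats acute GVHD in the same way.

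**The concern.** Being alive and relapse-free at day 100 is known only after randomisation, and a severe viral infection can prevent it. A patient with viral pneumonitis who dies on day 60 leaves both numerator and denominator, although that is an event the trial wants to prevent. Section 4.3 expects lower non-relapse mortality with individualised dosing, so the protocol itself expects removal to differ between arms. The remaining groups are then no longer the randomised groups.

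The sections also cannot all be followed. A cumulative incidence in all treated patients, a proportion among relapse-free survivors and, on a literal reading of the success sentence in 12.1, a composite of infection, death and relapse can give different primary results from the same data.

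**Working it through.** **Inputs.** From section 12.1: 40% infected in arm A, 15% in arm B (the numerators of the two fractions), 10% removed per arm, 42 evaluable per arm, two-sided 5%, pooled Z test, stated power 81%. The share of removed patients who were infected first is not given, so it is varied below as an assumption.

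**Formula.** Power = Φ[(|pA − pB| − 1.96·s0)/s1], with s0 = √(2p̄(1 − p̄)/n), s1 = √((pA(1 − pA) + pB(1 − pB))/n) and p̄ the mean of the two rates.

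**1. The protocol's figure.** pA = 0.4444, pB = 0.1667, n = 42: s0 = 0.1005, s1 = 0.0958, (0.2778 − 0.1970)/0.0958 = 0.84, power 80.0%. Simulating the same test gives 80.8%, so the stated 81% reproduces. Inflation: 42 × 1.15 = 48.3, rounded up to 49.

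**2. What 40/90 and 15/90 assume.** Per 100 patients, if a share f of the 10 removed had been infected first, the evaluable rate is (40 − 10·fA)/90 in arm A and (15 − 10·fB)/90 in arm B. The protocol's fractions need fA = fB = 0.

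| fA, fB (assumed) | Evaluable rates | Power, 42 per arm |
|---|---|---|
| 0, 0 (protocol) | 44.4% v 16.7% | 80.0% |
| 0.40, 0.15 (independence) | 40.0% v 15.0% | 73.6% |
| 0.80, 0.40 | 35.6% v 12.2% | 71.5% |
| 1.00, 0.15 | 33.3% v 15.0% | 50.1% |
| 0.50, 0.50 | 38.9% v 11.1% | 85.0% |

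Power falls when the removed patients carry more infections in arm A than in arm B, and rises when the shares are equal. These cases are illustrations, not limits.

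**3. Selection bias, with assumed rates.** Let infection be 40% in both arms and let 5% of uninfected patients die or relapse. If 25% of infected patients in A and 10% in B die or relapse, the survivors-only rates are:
- A: 0.40 × 0.75/(0.40 × 0.75 + 0.60 × 0.95) = 0.30/0.87 = 34.5%
- B: 0.40 × 0.90/(0.40 × 0.90 + 0.60 × 0.95) = 0.36/0.93 = 38.7%

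A difference appears where none exists. Exchanging the 25% and 10% reverses its sign, and giving both arms the same value removes it.

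**4. All treated patients.** If each patient is followed to infection, death, relapse or day 100, the day-100 cumulative incidence is a simple proportion and the same formula applies. At 40% v 15%, 49 per arm gives 80.1% and 45 per arm 76.6%. If 15% were still lost, 49/0.85 = 57.6, so 58 per arm would be needed.

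**5. Composite reading.** Adding the protocol's 10% to each arm gives 50% v 25%; 49 per arm has 73.1% power and 58 per arm would be needed.

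**The case against.** Section 12.1, read as a whole, agrees with 12.4.1: its success sentence is followed by a denominator that removes deaths and relapses, and only infections are counted as failures. The power arithmetic is correct for that endpoint. Both points stand. The firm conflict is therefore between two definitions, and the composite is only a literal reading of one sentence.

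The restriction might also be defended by the introduction's aim of bringing more patients to later interventions. That aim would call for counting infection-free, relapse-free survivors among everyone treated, not for conditioning on survival.

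Some stronger readings are tempting but not supported:
- A reader might infer that the bias must work against individualised dosing. Step 3 shows that this depends on how lethality differs by arm, which the documents do not give. The protocol's stated mechanism is fewer infections, not equally frequent but less lethal ones.
- A reader might take the 54% of non-relapse deaths attributed to infection (section 4.1.2) as the share of removed patients with a prior viral infection. It covers bacterial and fungal infections too, is not limited to day 100 and leaves out relapses. It also sits beside n=6, while the figure legend gives 13 deaths (6/13 = 46%).
- A reader might conclude that the most severe infections go uncounted. Grade 3 infections in relapse-free survivors are counted; only those in patients who die or relapse by day 100 are lost.
- A reader might conclude that power is necessarily overstated. The last row of the table shows a case where it is higher than stated.

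**Conclusion.** The concern holds. The protocol fixes conflicting primary endpoints itself, so this is not a detail left to a statistical analysis plan. The version chosen for analysis drops infected patients who die or relapse by day 100 and departs from the stated intention-to-treat population. The resulting comparison is open to selection bias of unknown size and direction.

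The fault in the power calculation lies in an input, not in the arithmetic. The stated power needs no overlap between infection and early death or relapse. Independence gives about 74% at 42 per arm, and the other assumed overlaps give roughly 50% to 85%. At 10% removal about 44 of 49 per arm would remain if nothing else were lost, and the independence figure would then be about 76%. The correction is warranted before analysis because it decides which patients enter the primary result.

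**What to change.** - **Section 12.4.1:** make the primary analysis the day-100 cumulative incidence of viral infection of grade 2 or higher (Appendix E) in all patients who started study treatment, as randomised. Death and relapse without prior infection are competing events; an infection that comes first stays an event. Keep the relapse-free-survivor analysis as a sensitivity analysis. This matches the synopsis, 5.1, 12.4 and the way the historical rate was obtained.
- **Section 12.1:** remove the success sentence and the division by 90, and restate the assumption as 40% v 15% of all treated patients. State that 49 per arm gives 80.1% power only if all are analysed, and about 77% at 45 per arm.
- **Section 10.7:** patients off study for graft failure or major protocol violation are now followed for survival only. Require infection data from them to day 100, and align the early-termination visit in 10.3.3.

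The cost is one amendment, some further data collection in patients who go off study, and loss of the 15% reserve for other losses. The 98 patients remain sufficient only if nearly complete day-100 infection status is obtained.
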